## 1. Summary

Title:	Development and Validation of an Artificial Intelligence-based Biliary Stricture Navigation System in MRCP-based ERCP
Short Title:	EndoAngel Study
Trial number:	EA-19-003
Research system	EndoAngel
Expected effect:	ENDOANGEL's intended use is to instruct the direction of guide wire and the position of stent placement in real time.
Primary Endpoint:	Procedure time
Secondary Endpoints:	
 
1. Intersection over union of bile duct segmentation
 
2. Intersection over union of bile duct matching model
 
3. Success rate of stent placement
 
4. Rate of adverse events
 
5. Fluoroscopy time
 
6. Total amount of contrast medium
 

Trail design:	Prospective, single-center, randomized controlled trial
Participants:	Male and female subjects aged 18 years or older will require MRCP and ERCP, and voluntarily provide imaging data of MRCP and ERCP, and sign an informed consent form.
Sample size:	62 samples needed to be enrolled
Study Process:	Subjects who met all inclusion criteria and did not meet all exclusion criteria were included in the study before ERCP. All included subjects signed an informed consent form. Subjects will be randomized prior to the start of the examination to either an Endoangel-assisted experimental group or a control group without Endoangel assistance. The operating physician completed ERCP according to the presence or absence of AI prompt. The recorder shall record procedure time, intersection over union of bile duct segmentation, intersection over union of bile duct matching model, success rate of stent placement, rate of adverse events, fluoroscopy time and total amount of contrast medium etc. Follow-up will be performed for one week after the end of examination. The end time of follow-up is the end time of study. And the results are sent to an independent data analysis team for review.

[figure not shown]

[figure not shown]
Security	Safety incidents shall be evaluated and reported according to the quality management measures for clinical trials of medical devices
-----------------	--

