## 3. Patient Selection

Male and female subjects aged 18 years or older will require MRCP and ERCP, and voluntarily provide imaging data of MRCP and ERCP, and sign an informed consent form.

Patients not meeting the inclusion criteria or meeting exclusion criteria will not be considered for participation in the study. Patients who met all criteria and signed informed consent may be excluded from the study due to:

- Endoscopists' professional advices/medical reasons (only under very limited conditions to avoid researcher bias).

- Withdraw informed consent.

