### **5.2. Overall design**

This is a prospective, single-center, randomized controlled trial study.

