## 6.5 Randomization and Blinding

### 6.5.1 Randomization Implementation

Randomization is conducted according to the study protocol, and the random contents are implemented in an electronic system block-randomized manner (n = 4; experimental group/control group = 1). Randomization prior to ERCP to decide whether to use EndoAngel. The researchers randomized the random results generated by the electronic system, and the generated random results were stored in the research center. The random time (accurate to minute), random person, subject number and acronym were recorded in the corresponding positions of the electronic system.

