### 6.5.2 Blinding Implementation and Protection

Subjects and evaluators are blinded according to the protocol.

Randomization results will be kept confidential to the subjects in general. Randomization results are not reflected in inpatient history and other subject access documents. During and after the examination, study personnel should take care not to talk to the subject about the results of the randomization to avoid unnecessary unblinding.

The assessors are blinded, and the data analysis team and pathologists could not obtain the randomization results from the medical history data.

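### Section 6.5.1 fixes and prints a single block size of 4 in a single-centre trial with unblinded operators, so anyone tracking the sequence could deduce up to one third of allocations in advance

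*Protocol*

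**What the plan says.** Section 6.5.1 sets an "electronic system block-randomized manner (n = 4; experimental group/control group = 1"). It gives the timing as "Randomization prior to ERCP to decide whether to use EndoAngel", and says that "the generated random results were stored in the research center". Section 5.2 states the setting: "This is a prospective, single-center, randomized controlled trial study". No stratification factor is named, so there is one running sequence.

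On blinding, section 6.5.2 says "Subjects and evaluators are blinded according to the protocol"; operators are not on that list. The Summary explains why they could not be: "The operating physician completed ERCP according to the presence or absence of AI prompt".

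On discretion, section 3 lets a patient who has met every criterion and consented still be left out for endoscopists' "professional advices/medical reasons (only under very limited conditions to avoid researcher bias"). Section 6.4.1 lets researchers withdraw a participant before the procedure on safety grounds. Neither section says whether the decision must come before the allocation is known.

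**The concern.** With a known block of 4 at 1:1, the last allocation in each block is always fixed by the first three. If the first two are alike, the third is fixed as well. An electronic system can hide the next code, but it cannot stop someone from working that code out from past codes and a known block size. Section 6.5.3 itself warns that uncovering one subject's result may leak those of others, and in this trial the operator learns the result in every case that he or she performs.

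The primary endpoint is procedure time, which plausibly depends on how hard the case is. If the next arm can be foreseen while there is still room to exclude, withdraw or defer a patient, easier cases could drift to one arm and harder cases to the other. Adjusting for recorded measures of difficulty would remove only part of such a bias.

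**Working it through.** **Inputs.** Block of 4, 1:1 (section 6.5.1). N = 62, SD 11.56 minutes, means 43.9 and 35 minutes, two-sided 5%, 80% power, 10% dropout (section 8.4). Only the absolute difference, 43.9 − 35 = 8.9 minutes, is used here. The n = 4 is read as block size; as a number of blocks it would give 62/4 = 15.5 patients per block.

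**1. The plan's own figure.** The protocol gives no predictability figure, only the sample size. The normal approximation gives n per arm = 2 × (1.960 + 0.842)² × 11.56² / 8.9² = 26.5, so 27. The exact t calculation gives 28 (power 80.8%). With 10% added, 56 × 1.1 = 61.6, so 62. The stated N reproduces.

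**2. Allocations known with certainty.** A 2:2 block has 6 equally likely sequences.
- Positions 1 and 2 are never certain.
- Position 3 is certain when the first two are alike, in 2 of 6 sequences = 1/3.
- Position 4 is always certain.

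The share is (0 + 0 + 1/3 + 1)/4 = 1/3. In 62 patients there are 15 full blocks plus 2 patients in positions 1 and 2, so the expected number is 15 × 4/3 = 20, or 20/62 = 32.3%.

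**3. Allocations guessed correctly**, always choosing the arm with more places left.
- Position 1: 1/2.
- Position 2: 2/3.
- Position 3: 1/3 × 1 + 2/3 × 1/2 = 2/3.
- Position 4: 1.

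The mean is (1/2 + 2/3 + 2/3 + 1)/4 = 17/24 = 70.8%, against 50% without blocks.

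**4. Illustrative bias, no true effect.** The shift s is an assumption. Expected time is s minutes shorter when the AI arm is known to be next and s minutes longer when control is known to be next, so the contrast between steered cases is 2s. If staff act in certain slots only, the bias is about 2s × 20/62. Type I error comes from simulation (N = 62, SD 11.56, two-sided t test).

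| Shift s | Bias, certain slots only | Share of 8.9 min | Type I error |
|---|---|---|---|
| ±3 min | 6 × 20/62 = 1.9 min (about 2) | 22% | about 10% |
| ±5 min | 10 × 20/62 = 3.2 min | 36% | about 18% |

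If staff also act on the better-than-even guess at position 2, the net share rises. That guess adds 2/3 − 1/3 = 1/3 per block, so the share is (15 × 5/3 + 1/3)/62 = 25.3/62. The bias is then 2.5 minutes for ±3 (type I error 12% to 13%) and 4.1 minutes for ±5 (about 26%). For ±1.5 it is 3 × 25.3/62 = 1.2 minutes, with about 6.6%.

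**5. What other block sizes do.** A known fixed block of 6 leaves 25% certain and 68.3% guessable; a known fixed block of 8 leaves 20% and 66.6%. With undisclosed mixed sizes of 4, 6 and 8 almost nothing is certain, but the simple guess rate over 62 patients falls only from about 70% to 68%.

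**The case against.** Several points on the other side stand.

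- One third is a ceiling. It applies to someone who follows every allocation in order. The protocol does not say how many operators there are, or that any of them sees the whole sequence. Section 6.2.1 gives screening and consent to the investigator or a trained designee, who need not be the operator. A reader might infer that the operator sees every past allocation; the documents show only that the operator knows the arm of the case in hand.
- A reader might also infer from "the generated random results were stored in the research center" that future codes are open to enrolling staff. The sentence does not say so, and custody of the list may be set in a separate specification. Section 6.5.1 does require the time, to the minute, and the person randomising to be recorded.
- Safeguards exist. Eligibility is assessed on days −30 to −1 and randomisation is on day 0 (section 1.1; sections 6.1 and 6.4 give the same order). Section 6.2.2 requires a screening record with reasons, section 6.2.3 forbids reuse of subject numbers, and section 6.4.3 bars replacement. Section 3 confines discretion to use "only under very limited conditions to avoid researcher bias".
- No document supports any particular shift in case difficulty.

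These points narrow the concern but do not remove it. A log makes steering traceable without preventing it. Section 3 does not say what its limited conditions are, and no section places the discretionary decision before allocation. Nothing in the protocol varies or withholds the block size.

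**Conclusion.** The point holds as a risk that the design creates without need. A single printed block size of 4, in one unstratified sequence with unblinded operators, makes up to one third of allocations (20 of 62) deducible and about 71% guessable by anyone who tracks the sequence. The untimed discretion in sections 3 and 6.4.1 leaves a way to act on that knowledge.

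The bias and type I error figures rest wholly on the assumed shift and on staff acting on it. They show sensitivity and are not a forecast. A reader might conclude that selection bias is present or that concealment has failed; the protocol shows opportunity only. The change is worth making before recruitment because it costs little, but the point does not invalidate the design.

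**What to change.** In section 6.5.1, replace the stated block size with randomly varying block sizes, kept in a restricted randomisation specification and not disclosed to enrolling or operating staff. In the same section, require that any discretionary exclusion under section 3 is decided and logged before the allocation is released, and that patients withdrawn after that stay in the arm to which they were randomised. The clinical grounds for exclusion or withdrawal need not change.

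Both parts are needed, because varying blocks mainly remove certainty and lower the simple guess rate only modestly. The cost is one setting in the existing electronic system and a few protocol sentences. The final arms may differ by a few patients, with negligible loss of power, and N stays at 62.

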### 6.5.2 Blinding Implementation and Protection

Subjects and evaluators are blinded according to the protocol.

Randomization results will be kept confidential to the subjects in general. Randomization results are not reflected in inpatient history and other subject access documents. During and after the examination, study personnel should take care not to talk to the subject about the results of the randomization to avoid unnecessary unblinding.

The assessors are blinded, and the data analysis team and pathologists could not obtain the randomization results from the medical history data.

### 6.5.3 Unblinding

Uncovering or breaking the blindness means displaying the randomized results to the subjects or evaluators. Researchers should protect the blind method as far as possible. Uncovering the randomized results of a single subject may lead to the leakage of the randomized results of other subjects. Any leakage of the randomized results will have a significant impact on statistical analysis. In general, it is prudent to deal with the disclosure of blind law. In the following cases, it is possible to consider the disclosure of blind law:

- 1) endangering the safety of subjects: For example, in some serious adverse events, subjects need to know the randomized results to inform other physicians to take appropriate emergency treatment.
- 2) Threatening the safety of the assessor: When the assessor is facing potential safety hazards, he needs to know the randomization results.
- 3) Compliance: For reasons of partial compliance, in certain circumstances, if the research instruments and cases involved in unexpected adverse events are needed, the results of randomization should be made public to the relevant departments or the public.
- 5) Other management reasons.

## 6.6 Concomitant therapy and medication

The concomitant treatment and concomitant medication were recorded from the time the subject signed the informed consent to the time the study was completed. Concomitant treatment and concomitant medication should be recorded in the CRF, or a clear copy of the form available from the research center should be kept in the CRF as research data to identify other factors affecting the end of the study. When recording the concomitant treatment and concomitant medication, the indications and the starting and ending time of use should be clearly defined, and the corresponding types of adverse events should be indicated for the treatment measures to cope with adverse events. When using a copy of the study center form, the investigator should sign the copy and indicate the date of review to confirm that the document is a study document.

## 7. Basis of study protocol and risk/benefit analysis

EndoAngel is used to provide assistant to monitor the operation of endoscopists, which will not provide diagnosis. Doctors make their own diagnosis on the basis of EndoAngel's results. The security of the software and the improvement of endoscopic physician's diagnosis and treatment level have also been confirmed in the previous feasibility study. And the patients in this study carry out the diagnosis and treatment according to the conventional treatment measures, which are formulated in accordance with the standard medical treatment procedures and do not increase the risk of the subjects.

### 7.1. Selection of endpoints

The primary endpoint is the procedure time.

The secondary endpoints were:1) Intersection over union of bile duct segmentation;2) Intersection over union of bile duct matching model;3) Success rate of stent placement;4) Rate of adverse events;5) Fluoroscopy time;6) Total amount of contrast medium.

Adverse events in safety indicators shall be judged in accordance with relevant regulations, and serious adverse events shall be recorded and reported in accordance with regulations.

Other evaluations are detailed in the Case Report Form (CRF).

### 7.2. Definition of participants

Patients were included according to the indications and contraindications described in the use

plan. Because of practical reasons (such as younger patients, participation in a number of clinical studies, alcohol/drug dependence patients, and other factors that may affect the completion and/or reliability of gastroscopy) and ethical reasons (whether informed consent can be completed, etc.), the entry and discharge criteria have been reduced.

### 7.3. Adverse events

The relevant definitions of adverse events are as follows:

**Adverse Events (AE):** Any adverse medical event, unexpected disease or injury, or adverse clinical manifestations (including abnormal laboratory findings) that occur in a subject, user or other person, whether or not associated with medical devices.

**Serious Adverse Events (SAE):** Adverse Events with the following information:

- causing death.
- leading to severe deterioration of the health of the subjects, including
- leading to life-threatening diseases or injuries,
- Causing impairment of body structure or function.
- Need hospitalization or extended hospitalization
- lead to hospitalization and preventive medical or surgical intervention
- Permanent damage to body structure or function
- Fetal distress, fetal death or congenital abnormalities or congenital defects.

Note: Hospitalization for existing conditions, or surgery required in the program, without serious deterioration of health status, is not considered a serious adverse event. Purposeful hospitalization, such as economic or reimbursement reasons, is not considered a serious adverse event.

**Unexpected adverse device response (UADE):** refers to adverse events related to medical devices that were not previously identified in the current version of the risk analysis report in terms of nature, severity or incidence. The definition includes any event caused by insufficient or inadequate description of the use or deployment of the device. This definition includes any event caused by a user's error.

### 7.4. Expected and trial-related adverse events

Previous studies have shown that the expected adverse events are basically the same as the complications of conventional endoscopic diagnosis and treatment.

The instrument used in this experiment is a medical software which is not in contact with human body. There is no difference between the experimental operation and the routine operation. The intervention measures (such as randomized process) in the experiment may slightly increase

the incidents of diagnosis and treatment.

### **7.5. Risk minimization**

In this study, when there are bugs in the software, doctors can still operate under their own judgment without affecting conventional diagnostic and treatment measures, greatly reducing the risk of the test.

### **7.6. Related benefits**

Subjects will be randomly assigned to an experimental group or a control group. And experimental subjects may improve the quality of ERCP.

### **7.7. Overall feasibility analysis**

EndoAngel is an independent system including both software and computer hardware, which can monitor image data 24 hours a day. The system is not invasive. The overall operability is strong.

## **8. Statistical Analysis**

### **8.1. Statistical Analysis Plan**

Data management and statistical analysis were implemented by Renmin Hospital of Wuhan University.

### **8.2. Methods**

Continuous variables should be described by number of subjects, mean, standard deviation, median, minimum and maximum. The classification variables are summarized by frequency and percentage.

### **8.3. Hypothetical test**

The main assumptions are:

1. The use of EndoAngel can reduce the operation time of ERCP;
2. The use of EndoAngel can improve the success rate of stent placement;
3. The use of EndoAngel can reduce the rate of adverse events;
4. The use of EndoAngel can reduce the fluoroscopy time;
5. The use of EndoAngel can reduce the total amount of contrast medium.

## 8.4. Sample Size Calculation

We mainly studied the effect of EndoAngel on the quality of ERCP for physicians. Therefore, data collection and analysis were conducted for the main effect. It is expected that a total of 62 subjects will be enrolled. Assuming the operation time of ERCP in experimental group is  $43.9 \pm 11.56$  minutes, the operation time of ERCP in control group is 35 minutes. Bilateral significance level 5% ( $\alpha = 5\%$ ), assurance 80% ( $\beta = 20\%$ ), shedding rate 10%, Expected to enroll 62 patients in total.

## 8.5. Statistical analysis set

All patients who met the inclusion and exclusion criteria were considered eligible for recruitment.

The two analysis sets in this study are defined as follows:

- The full analysis set (FAS) population analysis set will contain all eligible cases and shedding cases, but does not include culling cases.
- The Compliance (PP) population analysis set will include all subjects in the FAS analysis set with no significant deviation from the program.

Intention-to-treat and conformity analysis sets should be used to analyze the primary efficacy endpoints. The main analysis will be based on the PP analysis set. FAS analysis was regarded as supportive analysis.

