### **6.4 Suspension and withdrawal**

Patients who were screened and confirmed to be eligible for the study, signed the informed consent and completed the randomization were considered as enrolled. If serious program deviation, withdrawal, or death occurs, the subject study is considered to be suspended. If the subject discontinues the study after obtaining informed consent, the data before the discontinuation will still be included in the study-related analysis.

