## 10. Abbreviations

Abbreviations	Full Name	Chinese
AE	Adverse Event	不良事件
CFDA	China Food and Drug Administration	国家食品药品监督管理总局
CNDA	China National Drug Administration	国家食品药品监督管理总局
CRF	Clinical Record File	病例报告表
CTCAE	Common Terminology Criteria for Adverse Events	不良事件常规评价标准
EC	Ethical Committee	伦理委员会
ICD	Informed Consent Document	知情同意文件
ICF	Informed Consent Form	知情同意书

ITT	Intention to Treat	意向治疗分析集
PP	Per Protocol	符合方案集
SAE	Serious Adverse Event	严重不良事件
ERCP	Endoscopic Retrograde Cholangiopancreatography	经内镜逆行性胰胆管造影术
MRCP	Magnetic Resonance Cholangiopancreatography	磁共振胰胆管造影

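### Section 8.5 makes the per-protocol set the main analysis of a superiority-type comparison of procedure time, and does not settle whether patients withdrawn after randomisation stay in it

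*Protocol*

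**What the plan says.** Protocol section 8.5 introduces its populations with "The two analysis sets in this study are defined as follows" and then gives two:

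- The full analysis set (FAS) "will contain all eligible cases and shedding cases, but does not include culling cases".
- The per-protocol (PP) set takes "all subjects in the FAS analysis set with no significant deviation from the program".

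It continues: "Intention-to-treat and conformity analysis sets should be used to analyze the primary efficacy endpoints". The order of priority follows: "The main analysis will be based on the PP analysis set. FAS analysis was regarded as supportive analysis". The only other mention of ITT is its expansion, "Intention to Treat", in section 10.

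Other sections bear on who ends up in these sets:

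- Section 3.3 places randomisation before ERCP and equates it with enrolment.
- Section 6.4.1 allows withdrawal before the procedure.
- Section 6.4.2 allows withdrawal during the procedure, including when the endoscopist does not use the specified instrument, and for perforation, bleeding or an ERCP that cannot be completed.
- Section 6.4 says "If serious program deviation, withdrawal, or death occurs, the subject study is considered to be suspended", and also that "the data before the discontinuation will still be included in the study-related analysis".
- Section 6.4.3 rules out replacement.
- Section 6.5.2 lists subjects and evaluators as blinded, not the operator. Under section 1 the operator works with or without the AI prompt.

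**The concern.** Section 8.3 expects EndoAngel to shorten ERCP. Section 8.4 sizes the trial for a difference at a two-sided 5% level. No non-inferiority or equivalence margin appears that could justify leading with PP. The protocol does not use the word superiority, but that is what the comparison is.

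A PP set is chosen by what happens after randomisation. Two of the reasons for withdrawal matter here. Non-use of the device falls mainly on the EndoAngel arm. An ERCP that cannot be completed bears directly on procedure time, the primary endpoint. Someone who knows the allocation can influence both. If either reason removes a patient from PP, the arms compared in the primary analysis are no longer the arms that were randomised, and with about 31 patients per arm a few removals are enough to matter.

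**Working it through.** **1. The plan's own figure.** Inputs from 8.4: means 43.9 and 35 min, SD 11.56 (taken as common to both arms), two-sided 5%, power 80%, shedding 10%. Only the absolute difference, 43.9 − 35 = 8.9 min, is used. The protocol names no test; a pooled t-test is assumed.

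- Normal approximation: n = 2 × (1.960 + 0.842)² × 11.56² / 8.9² = 26.5, so 27 per arm.
- t-test: 27.5, so 28 per arm, 56 in total. 56 × 1.1 = 61.6, so 62.

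The stated 62 reproduces. The point does not rest on a sample-size error.

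**2. Who is in the primary set.** Section 8.5 removes significant deviations from PP but does not say whether withdrawal or non-use is one. Section 6.4 points both ways: it lists serious deviation and withdrawal as separate events, and it keeps data collected before discontinuation without naming the analysis. That withdrawn patients leave PP is therefore an inference, not a stated rule.

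**3. Scale, if they do leave PP.** Simulation of 100,000 trials: no true effect, normal times with mean 43.9 and SD 11.56 in both arms, 31 per arm, t-test. The loss of up to 3 per arm is an assumption (about 10%, borrowed from the shedding rate; 3/31 = 9.7%). The percentages are false wins for the arm that loses more.

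- No loss, or 3 lost at random from each arm: 0 min, 2.5%.
- 3 longest lost from each arm: 0 min, about 4% in each direction.
- 3 longest against 2: 0.6 min, about 6%.
- 3 longest against 1: 1.3 min, about 8%.
- 3 longest against 0: 2.1 min, about 12%. This is the extreme case.
- 3 at random from the slowest 10 of one arm only: about 1.35 min, 6.5%.

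The results mirror when the other arm loses more.

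**4. Why aborted procedures must be handled in the same change.** Assume 3 of 31 procedures that would have run 60 min are stopped at 15 min (both times assumed).

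- Uncut arm mean: (28 × 43.9 + 3 × 60)/31 = 45.46 min.
- Excluding the three: 43.9 min, a shift of −1.56.
- Keeping 15 min at face value: (28 × 43.9 + 3 × 15)/31 = 41.10 min, a shift of about −4.35.

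With 3 such cases in each arm, aborted only in the EndoAngel arm, false EndoAngel wins are about 22% when the 15 min is kept and about 6 to 7% when the three are excluded. Changing the set without a rule on aborted times can therefore do worse than PP.

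**5. Power at 8.9 min, t-test.** All 62 with a procedure time: 84.7%. With 56: 80.8%. If EndoAngel is not used in k of 31 patients and they gain nothing from it, the difference becomes 8.9 × (31 − k)/31:

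- k = 1: 8.61 min, 82.3%.
- k = 2: 8.33 min, 79.7%.
- k = 3: 8.04 min, 76.8%.

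**The case against.** Several points can be made for the protocol, and most of them stand in part.

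- **The set names.** A reader might infer that a third, undefined ITT set is required. With two sets defined and two named for the primary endpoint, the natural reading is loose naming: conformity is PP and intention-to-treat is the FAS. This is a lesser wording point.
- **Culling.** A reader might infer that the FAS drops inconvenient cases. The documents do not support that. The FAS keeps dropouts, and the excluded cases may be only patients found ineligible. What remains is that no criteria are given, so the FAS is not clearly all randomised patients.
- **Section 3.** Its exclusion on the endoscopist's advice could be read as a route out after randomisation. It stands under patient selection and may well apply only before randomisation.
- **Partial protection.** Section 6.4 retains earlier data, 6.4.3 bars replacement, and the FAS is still analysed alongside PP. This softens the harm but leaves the primary set unsettled.
- **The size.** No deviation rate is documented, and the 10% is dropout, not selective loss of long cases. Most withdrawal rules apply to both arms, and equal losses roughly cancel. A reader might infer bias in favour of EndoAngel; the documents do not establish a direction.
- **SAP territory.** A list of deviations and missing-data methods can be left to an SAP. The order of priority cannot be set aside that way, because 8.5 fixes it.

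**Conclusion.** The point holds as a stated choice of the wrong lead analysis: 8.5 puts PP first and the FAS second for a superiority-type comparison in which the operator is not listed as blinded. That part rests on the text alone. The harm is conditional. It requires that patients withdrawn under 6.4, or not treated with the device, count as significant deviations, and that the losses are selective and unequal between arms. Under the assumed losses of the longest cases, false wins rise from 2.5% to between about 6% and 12%; under random loss they do not rise at all. Neither size nor direction can be read from the documents. The choice should still be corrected before any arm-level data are seen, because it decides who counts in the primary result and cannot credibly be changed afterwards.

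**What to change.** In section 8.5:

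1. Make the primary set all randomised patients in their allocated arm, under one name (ITT/FAS), and make PP supportive.
2. Limit culling to ineligibility established from pre-randomisation data, without knowledge of arm or outcome.
3. State that withdrawal under 6.4, or non-use of EndoAngel, does not by itself remove a patient from the primary set. Reconcile this with 6.4 by naming the analysis meant there. The clinical withdrawal rules stay as they are.
4. As part of the same change, state that the time of an aborted ERCP is not taken at face value as a short procedure, and that patients without a procedure time are reported by arm and reason. The method can be left to the SAP.

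**Cost.** Text changes and no new data. N stays 62 unless the scoring chosen for aborted cases calls for a recalculation. Worst-rank scoring with a rank-sum test, for example, would: simulated power with 31 per arm is about 79% with 1 failure per arm and 67% with 3, and about 10% failures would need roughly 41 per arm (82 in total) for 80%. The 84.7% above applies only if all 62 have a procedure time, which patients withdrawn before ERCP cannot have. Keeping non-users in the primary set brings power to about 82%, 80% or 77% for 1, 2 or 3 of 31.
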